| Brief Summary | This is a first-in-human, safety and feasibility study of bronchoscopic cryo- immunotherapy (BCI) of peripheral lung tumors in advanced non-small cell lung cancer (NSCLC) and suspected NSCLC. BCI has the potential to stimulate anti-tumor immune responses. Pre- and post-BCI peripheral blood samples will be analyzed to assess for anti-tumor immune responses. Post- BCI peripheral blood will be collected 7 and 14 days after the procedure. Additionally, pre-BCI bronchoalveolar lavage (BAL) specimens will be collected to correlate PD-1 phenotype on pre-BCI BAL lymphocytes by single cell RNA sequencing and BCI-induced anti-tumor immune responses. | | |
| Phase | Phase I | | |
| Objectives Primary: • Establish safety and feasibility of BCI and determine the maximu tolerated dose (MTD) (i.e., freeze duration) Secondary: | | | |
| Assess the extent of BCI-induced anti-tumor immune respons | | | |
| Methodology Dose-escalation trial using a 3+3 design Primary: Feasibility and Safety | | | |
| | Feasibility: successful performance of BCI in at least 80% of participants in whom BCI is attempted Safety endpoints: Dose-limiting toxicity (DLT), defined as incidence of bleeding complications and pneumothorax, length of time to perform BCI, length of fluoroscopy exposure during BCI, and other adverse events | | |
| Endpoints | Secondary: Immune Analysis and Tumor Response Changes in peripheral blood CD8⁺ T cells expressing a combination of Ki67⁺,PD-1+, HLA-DR⁺, CD38⁺, and Bcl-2^{low} after BCI Changes in peripheral blood lymphocyte gene expression after BCI, which will be assessed by the PanCancer OncolmmuneTM profile panel, a 770-plex gene expression panel covering innate and adaptive immune responses (NanoString® Technology, Seattle, WA) Correlation of PD-1 phenotype of pre-BCI BAL lymphocytes by single-cell RNA sequencing and BCI-induced anti-tumor immune responses. | | |
| Study Duration 12 months | | | |
| Participant Duration | 14 days | | |
| Duration of IP administration | BCI will be performed once at the time of a standard-of-care bronchoscopy for another indication. BCI is anticipated to take approximately 15-25 minutes. | | |

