3.1 Primary Objective: Demonstrate Feasibility and Determine the MTD

1) Demonstrate feasibility of BCI

We hypothesize that BCI will be feasible, defined as successful performance in at least 80% of patients in whom BCI is attempted. Successful performance of BCI will require identification of the target peripheral lung tumor by radial endobronchial ultrasound within 20 minutes followed by completed cryoablation of target tumor.

2) Determine the safety and MTD of BCI

We hypothesize that BCI will prove safe at each planned dose level. Using a standard 3+3 design, the trial will determine the maximally tolerated dose (MTD) by sequentially assessing increasing freeze times during the procedure. Dose-limiting toxicity (DLT) is defined as the occurrence of any of the following: grade 2 or 3 bleeding, pneumothorax necessitating tube thoracostomy, or any NCI CTCAE grade 4 or 5 adverse events, which may be possibly, probably, or definitely related to BCI (33). The monitoring period for dose limiting toxicity will be for seven days post-BCI.

3.2 Secondary Objectives: Assess BCI Induced Anti-Tumor Immune Responses1) Pre- and Post-BCI Peripheral Blood Analysis

We hypothesize that BCI will induce activation and proliferation of peripheral blood T cells. Based on previous work (26, 27) (see section 2.1.IV for full details), we hypothesize that some combination of the following markers will be displayed on peripheral blood CD8⁺ T cells after BCI: HLA-DR and CD38 (surface markers of CD8⁺ T cell activation), Ki-67 (a cell cycle marker of proliferation), Bcl-2 (an anti-apoptotic protein downregulated on activated CD8⁺ T cells), and PD-1. We also hypothesize that there will be significant changes in peripheral blood lymphocyte gene expression after BCI, which will be assessed by the PanCancer OncoImmune[™] profile panel, a 770-plex gene expression panel covering innate and adaptive immune responses (NanoString® Technology, Seattle, WA).

2) Investigate BCI Association with PD-1 Phenotype of Effector T cells in NSCLC

We hypothesize that BCI will induce PD-1 phenotype in circulating effector T cells on single-cell RNA sequence analysis and that CD8+ T cell responses to BCI will be greater among subjects with high PD1 expressing T cells in BAL effluent.

4 Study Design and Endpoints

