4.2 Study Endpoints

4.2.1 Primary Study Endpoints: Feasibility and Safety

- Each patient will be classified as having successfully undergone BCI or not. Feasibility of BCI is defined as successfully performing BCI in at least 80% of patients in whom BCI is attempted. Successful performance of BCI will require identification of the target peripheral lung tumor by radial endobronchial ultrasound within 20 minutes followed by completed cryoablation of target tumor. The target tumor will have freeze-thaw cycles applied every one centimeter of the largest diameter. Additional BCI features will be described as follows:
 - a) Ability of radial endobronchial ultrasound to identify peripheral lung tumor
 - b) Length of time to perform BCI
 - c) Length of time of fluoroscopy exposure during BCI
- 2) Dose-limiting toxicities (DLT) will be used to guide the dose-escalation procedure and determine the maximum tolerated dose. A DLT is defined as any of the following occurring up to 7 days post-BCI:
 - Grade 2 or 3 bleeding, based on the following scale (34):
 - a) Grade 0: absence of bleeding
 - b) Grade 1: bleeding requiring suctioning to clear
 - c) Grade 2: bleeding requiring an endoscopic procedure (iced saline, 1:20,000 topical epinephrine, or bronchial occlusion)
 - d) Grade 3: severe bleeding (>100cc total volume). Severe bleeding will also be defined as bleeding which cannot be controlled endoscopically, requires ICU admission or interventional radiology/ surgical intervention, or results in respiratory or hemodynamic instability (34)
 - Pneumothorax necessitating tube thoracostomy; recorded features of pneumothorax to include:
 - a) size
 - b) associated symptomatology
 - c) respiratory impairment
 - d) need for chest tube placement
 - Any NCI CTCAE (33) grade 3, 4, or 5 adverse events, which may be possibly, probably, or definitely related to BCI

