6.1.2 Dose Escalation Protocol

A standard 3+3 dose escalation strategy will be used. The table below shows the doses that will be provided. Three participants will be initially enrolled at Level 1. If none of the first three participants at a given dose experiences dose-limiting toxicity (DLT), the dose will be escalated. If two or more of the first three participants experience DLT, the prior dose will be deemed the maximum tolerated dose (MTD) and the study will be terminated. If one of the first three participants experiences DLT, an additional three participants will be enrolled at the same dose. If among these six, only one experiences DLT, the dose will be terminated. If two or more of six experience DLT, the prior dose will be deemed the MTD and the study will be terminated. If the MTD is reached and only three participants have been treated at that dose, an additional three will be treated to ensure six subjects are treated at the MTD. DLT are defined in Section 4.1.1 (Primary Study Endpoints: Feasibility and Safety).

| Dose Level | Freeze Time (per site) | Thaw Time |
|------------|------------------------|---|
| Level 1 | 1 second | Will last until the probe separates from target tissue* |
| Level 2 | 2 seconds | Will last until the probe separates from target tissue* |
| Level 3 | 3 seconds | Will last until the probe separates from target tissue* |
| Level 4 | 5 seconds | Will last until the probe separates from target tissue* |
| Level 5 | 10 seconds | Will last until the probe separates from target tissue* |
| Level 6 | 20 seconds | Will last until the probe separates from target tissue* |

CONFIDENTIAL

| Level 7 | 30 seconds | Will last until the probe separates from target |
|---------|------------|---|
| | | tissue* |

6.1.3 **Procedures for Training of Clinicians on Procedural Intervention**

The NYU Interventional Pulmonary service has extensive experience using the flexible cryoprobe for debulking of central airway tumors. BCI will be performed by a board-certified, NYU Interventional Pulmonologist.

Only patients with the presence of a bronchus or airway path leading directly to the peripheral lung tumor will be eligible to undergo BCI. The peripheral tumor will also need to be identified by radial EBUS prior to performing BCI. If the peripheral tumor is unable to be identified by radial ultrasound within 20 minutes, then the patient will not be a candidate to undergo BCI.

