8.1 Specification of Safety Parameters

Dose-limiting toxicities (DLT) will be used to guide the dose-escalation procedure and determine the maximum tolerated dose. A DLT is defined as any of the following occurring up to 7 days post-BCI:

- Grade 2 or 3 bleeding, based on the following scale (34):
 - a) Grade 0: absence of bleeding
 - b) Grade 1: bleeding requiring suctioning to clear
 - c) Grade 2: bleeding requiring an endoscopic procedure (iced saline, 1:20,000 topical epinephrine, or bronchial occlusion)
 - d) Grade 3: severe bleeding (>100cc total volume). Severe bleeding will also be defined as bleeding which cannot be controlled endoscopically, requires ICU admission or interventional radiology/ surgical intervention, or results in respiratory or hemodynamic instability (34)
- pneumothorax necessitating tube thoracostomy; recorded features of pneumothorax to include:
 - a) size
 - b) associated symptomatology
 - c) respiratory impairment
 - d) need for chest tube placement
- any NCI CTCAE (33) Grade 3, 4, or 5 adverse events, which may be possibly, probably, or definitely related to BCI

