8.3 Reporting Procedures

8.3.1 Adverse Event Reporting

Any adverse events or serious adverse events possibly, probably, or definitely related to BCI will be reported in real-time notification by the clinical investigators to the Data and Safety Monitoring Board and Data Coordinating Center. In accordance with 21 CFR 812.150(a)(1), the clinical investigators will also report to the IRB as soon as possible and within 10 working days.

In the event of any unexpected fatal or life-threatening suspected adverse reaction, the Data and Safety Monitoring Board and IRB will be notified as soon as possible and within 2 working days.

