8.5.1 Data Safety Monitoring Board (DSMB)

Safety oversight will be under the direction of a Data Safety Monitoring Board (DSMB) composed of [name] (Associate Chief of Staff for research at the VA NY Harbor Healthcare System and Associate Professor in the Division of Pulmonary, Critical Care, and Sleep Medicine) and [name] (Deputy Director of the Perlmutter Cancer Center and Professor of Oncology).

The members of the DSMB have appropriate medical and research expertise, and are not involved in this study. The DSMB will meet at least semiannually to assess safety and efficacy data on each research subject undergoing BCI. The primary responsibilities of the DSMB will be to periodically review and evaluate the accumulated study data for participant safety, study conduct and progress, and make recommendations concerning the continuation, modification, or termination of the trial. Pre-defined stopping rules are described in Section 8.4: Study Halting Rules. The outcome of each DSMB review and decision made (eg, continuing the study, continuing with modifications, suspending the study, or terminating the study) will be submitted to the IRB.

[name] will serve as a medical monitor who be responsible for overseeing participant safety. [name] has extensive expertise in both bronchoscopy and translational research. He will 1) review all AEs (including DLT and unanticipated events) on a regular basis throughout the trial; 2) be available to advise the investigators on trial-related medical questions or problems, and 3) evaluate cumulative participant safety data and make recommendations regarding the safe continuation of the study. He will identify/evaluate AE/SAEs, determine seriousness, severity, causality, and monitor and follow subjects to resolution. He will report the events and will notify the IRB. In the event of DLT, the IRB will be notified as soon as possible and within three days.

9 Clinical Monitoring

Clinical site monitoring is conducted to ensure that the rights and well-being of human subjects are protected, that the reported trial data are accurate, complete, and verifiable, and that the conduct of the trial is in compliance with the currently approved protocol/amendment(s), with GCP, and with applicable regulatory requirement(s).

- Monitoring for this study will be performed by an assigned medical monitor
- On-site monitoring will take place throughout the study, which will include a comprehensive review of all data and safety

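### Section 3.1 makes a related CTCAE event a DLT only at grade 4 or 5, but the definition that drives escalation (4.2.1 and 8.1) starts at grade 3

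*Combined protocol and SAP*

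**What the plan says.** The protocol states the CTCAE part of the DLT definition three times.

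- **Section 3.1** (primary objective): "any NCI CTCAE grade 4 or 5 adverse events", if at least possibly related to BCI.
- **Section 4.2.1** (primary endpoints): "grade 3, 4, or 5 adverse events, which may be possibly, probably, or definitely related to BCI".
- **Section 8.1** (safety parameters): "Grade 3, 4, or 5 adverse events, which may be possibly, probably, or definitely related to BCI".

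The rest of the definition agrees in all three places: grade 2 or 3 bleeding, pneumothorax needing tube thoracostomy, the relatedness categories and the seven-day window.

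Sections 4.2.1 and 8.1 both say that their DLTs "will be used to guide the dose-escalation procedure and determine the maximum tolerated dose". The escalation rule in 6.1.2 says "DLT are defined in Section 4.1.1 (Primary Study Endpoints: Feasibility and Safety". That title belongs to 4.2.1 alone; the cited number does not exist. The Protocol Summary speaks of "Dose-limiting toxicity (DLT), defined as incidence of bleeding complications and pneumothorax" together with other items and gives no CTCAE grade for a DLT, so it does not settle the matter.

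**The concern.** The DLT count decides every step of the 3+3 design and the two-DLT termination rule in 8.4, and so determines the MTD, which is a primary objective. Section 3.1 gives a full definition rather than a loose paraphrase, and a reader who relied on it would leave out related grade 3 events. After the first three participants at a level, *add three* or *stop* could become *escalate*, or *stop* could become *add three*.

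The same threshold sets a reporting deadline. Section 8.5.1 says "In the event of DLT, the IRB will be notified as soon as possible and within three days". For a related adverse event that is not a DLT, 8.3.1 says "the clinical investigators will also report to the IRB as soon as possible and within 10 working days", unless it is also an unanticipated problem, which 8.3.2 puts at 3 days. These are outer limits, but the limit for a grade-3-only event depends on which definition is used.

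**Working it through.** **Which definition governs.** Section 6.1.2 points by title to 4.2.1. Section 8.1 repeats the 4.2.1 threshold, and both say that it guides escalation. No escalation, halting or analysis section refers to 3.1 for the definition. The text therefore identifies grade 3, 4 or 5 as operative and 3.1 as the outlier.

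**The plan's own figures.** The table in 10.5 gives the probability of escalation by true DLT rate *p*. The standard 3+3 formula is (1−p)³ + 3p(1−p)²·(1−p)³. At p = 0.10 this is 0.729 + 0.177 = 0.906, against a stated 0.91. The entries from 20% to 70% also reproduce (0.709, 0.494, 0.309, 0.172, 0.082, 0.032). The table is indexed by the DLT rate, so correcting 3.1 changes none of it; the choice of definition changes which rate applies.

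**Size of the discrepancy if 3.1 were used.** The documents give no rates, so these inputs are assumptions:

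- *c*, the probability of a DLT under both definitions: 0, 0.05 or 0.10.
- *g*, the probability of a related grade-3-only event among participants without such a DLT: 0.01 or 0.02.

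The rule in 6.1.2 for the first three participants is: no DLT, escalate; one, add three; two or more, stop. The decision under 3.1 differs from that under 4.2.1 in two situations:

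1. No participant has a common DLT and at least one has a grade-3-only event: (1−c)³[1−(1−g)³].
2. Exactly one has a common DLT and at least one of the other two has a grade-3-only event: 3c(1−c)²[1−(1−g)²].

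At c = 0.05, g = 0.01: 0.857375 × 0.029701 + 0.135375 × 0.0199 = 0.02546 + 0.00269 = 0.0282.

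At c = 0.05, g = 0.02: 0.857375 × 0.058808 + 0.135375 × 0.0396 = 0.05042 + 0.00536 = 0.0558.

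| c | Decisions differ, g = 0.01 | Decisions differ, g = 0.02 |
|---|---|---|
| 0 | 0.0297 | 0.0588 |
| 0.05 | 0.0282 | 0.0558 |
| 0.10 | 0.0265 | 0.0525 |

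At c = 0.05 the differences split as follows:

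| Under 3.1 | Under 4.2.1 and 8.1 | g = 0.01 | g = 0.02 |
|---|---|---|---|
| Escalate | Add three | 0.0252 | 0.0494 |
| Add three | Stop | 0.0027 | 0.0054 |
| Escalate | Stop | 0.0003 | 0.0010 |

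At c = 0.05 the DLT rate is 0.05 under 3.1 and 1 − 0.95(1−g) = 0.0595 or 0.0690 under 4.2.1 and 8.1.

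This calculation stops at the first-three decision. It therefore does not depend on what 6.1.2 means when it says that the dose is terminated after one DLT in six.

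**The case against.** The strongest reply is that this is close to clerical. The operative rule can be recovered from the text, it is the more cautious one, and staff working from 6.1.2 or 8.1 would reach it. Every harm listed requires someone to apply 3.1 instead. The safeguards are also real: one site, one medical monitor who reviews all adverse events including DLTs, related events reported to the DSMB in real time, and a suspension in 8.4 after three grade 3 events judged probably related. This stands, and it limits the risk. It does not remove the need to act: a complete but wrong definition sits in the primary objective, and the pointer that would resolve it carries a section number that does not exist. The 8.4 suspension is only a partial backstop, since one event is enough to change a cohort decision.

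A second reply is that the separate grade 3 rule in 8.4 may mean grade 3 events were meant to be handled outside the DLT definition. The two are compatible, because the 8.4 count can build up across dose levels while a DLT is counted within one. It is still sensible for the sponsor to confirm the intended grade.

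A third reply is that the size depends wholly on the assumed rates. That is correct. With grade-3-only events adding 5, 10 or 20 percentage points to a 10% DLT rate, the 10.5 formula gives an escalation probability of 0.814, 0.709 or 0.494 instead of 0.906. The percentages illustrate the effect and do not estimate it.

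**Conclusion.** The concern holds and should be fixed. Section 3.1 contradicts 4.2.1 and 8.1 on the CTCAE grade that makes a related event a DLT, and the text shows 3.1 to be the wrong one. The effect is confined to participants whose only qualifying event is a related grade 3 event outside the bleeding and tube-thoracostomy criteria.

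Under the assumed rates, using 3.1 would change the first-three decision in roughly 3% of cohorts at a grade-3-only rate of 1%, and in 5-6% at a rate of 2%. At a common DLT rate of 5%, most of these would escalate when three more participants should be enrolled at the same dose. The inconsistency itself rests on no assumption; only its size does.

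**What to change.** In 3.1, change the threshold to grade 3, 4 or 5, or replace the definition with a reference to 4.2.1. The sponsor should confirm the intended grade when making the change.

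As a clerical matter, correct 4.1.1 to 4.2.1 in 6.1.2 and 10.4.3. Two similar slips can be corrected at the same time: 7.2.1 cites 4.1.2 for 4.2.2, and 10.4.3 cites 6.1.1 for the escalation rules in 6.1.2.

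Separately, the suspension trigger in 8.4 counts three grade 3 events judged probably related and, as worded, leaves out those judged definitely related, which 8.2.2 treats as the stronger category. It should cover both.

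The cost is one phrase in 3.1, a few section numbers and two words in 8.4. No extra data or participants are needed.

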2.2.3 BCI Dose Rationale

BCI of peripheral lung tumors has not been performed previously. To maximize safety, the initial freeze time is shorter than standard freeze times for cryobiopsy of peripheral lesions (15). Our dose escalation will initiate patients at a safe freeze time for which there is extensive clinical experience with related procedures. If there is no complication from this, in the next cohort of patients we will gradually escalate dose to those higher than are routinely performed in bronchoscopic cryobiopsy.

CONFIDENTIAL

Freeze times will be escalated up to 30 seconds based on tolerability. In comparison, freeze times of up to 20 minutes have been safely administered during percutaneous cryoablation of peripheral lung tumors (7, 10). Although an optimal freeze time duration is unknown, longer freeze times may be needed in order to induce anti-tumor immune responses. Based on tolerability, freeze times will be increased as described in the following table:

| Dose Level | Freeze Time (per site) | Thaw Time |
|------------|------------------------|---|
| Level 1 | 1 second | Will last until the probe separates from target |
| | | tissue* |
| Level 2 | 2 seconds | Will last until the probe separates from target |
| | | tissue* |
| Level 3 | 3 seconds | Will last until the probe separates from target |
| | | tissue* |
| Level 4 | 5 seconds | Will last until the probe separates from target |
| | | tissue* |
| Level 5 | 10 seconds | Will last until the probe separates from target |
| | | tissue* |
| Level 6 | 20 seconds | Will last until the probe separates from target |
| | | tissue* |
| Level 7 | 30 seconds | Will last until the probe separates from target |
| | | tissue* |

* Thaw times at each dose level will be captured for each site.

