mRNA analysis: We will also be assessing a variety of other immune biomarkers from peripheral blood utilizing the NanoString[™] platform, including cytokine gene expression, that may allow for the establishment of a variety of peripheral blood biomarkers to correlate with the effects of BCI in advanced NSCLC. Once sorted, the CD8+ and CD4+CD25- cells (non-Treg cells) will be processed for RNA extraction and NanoString[™] mRNA quantitation. RNA extraction will be performed using the MARIS technique to insure RNA quality after sorting (35). We are particularly interested in determining gene expression of proteins involved in T cell activation and immune regulation, such as CTLA-4, PD-1, OX-40, TIM-3, IL-10, TGF-ß, IL-2, MHC-II and TNF-α. The transcriptome data will be processed in collaboration with the Biostatistics Division led by [name] at the NYU School of Medicine to calculate the relative expression of the key genes of interest previously noted. The NanoString[™] platform offers the convenience of straightforward high-throughput mRNA quantitation using RNA barcodes to probe and count mRNA transcripts of interest (28). Our preliminary analysis will be conducted with the pre-designed Oncolmmune[™] Profile panel, which measures 770 gene targets most relevant in tumor immunobiology.

2) Investigate BCI Association with PD1 phenotype of Effector T cells in NSCLC

Research Samples: In addition to peripheral blood specimens as described previously, BAL fluid will be collected from regions of the primary tumor and of the distal portion of the same lung.

Using a subset of samples from enrolled subjects enrolled with sufficient BAL specimens, we will perform single-cell RNA sequencing on sorted CD3+ T cells from BAL and PBMCs obtained at the time of BCI. This approach will be repeated in PBMC after 7 and 14 days post BCI. The percentage of PD-1 expressing T lymphocytes will be determined in CD4⁺ and CD8⁺ cells from both BAL and PBMC compartments. PD1⁺ cell percentage and transcriptome will be compared between responder categories. RNA sequencing and subsequent data analysis will be performed in the Genomic Technology and Bioinformatics Cores of NYU School of Medicine.

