4.2.3 Sub-Set Analysis and Exploratory Endpoints

- Investigation of changes in peripheral blood CD8⁺ T cells displaying a combination of Ki67⁺, PD-1+, HLA-DR⁺, CD38⁺, and Bcl-2^{low} after BCI at each dose level. This sub-set analysis will investigate if there is an optimal freeze time duration for inducing anti-tumor immune responses.
- 2) Investigation of changes in peripheral blood CD8⁺ T cells displaying a combination of Ki67⁺,PD-1+, HLA-DR⁺, CD38⁺, and Bcl-2^{low} after BCI at each dose level. This sub-set analysis will investigate if the combination of cryoablation and current active cancer treatment will lead to enhanced increases in percent of peripheral blood CD8⁺ T cell expression of PD-1 and Ki67 and/or CD8⁺ T cells displaying an activated effector-like phenotype.

5 Study Enrollment and Withdrawal

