10.2 Statistical Hypotheses

- 1) BCI will be feasible and safe, with a maximum tolerated dose to be determined in this trial.
- 2) Post-BCI peripheral blood will demonstrate an increase in the percent of CD8⁺ T cells expressing a combination of Ki67⁺, PD-1+, HLA-DR⁺, CD38⁺, and Bcl-2^{low} compared to pre-BCI peripheral blood CD8⁺ T cells.
- 3) CD8+ T cell responses to BCI will be greater among subjects with high PD-1 expressing T cells in BAL effluent.

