10.4.4 Analysis of the Secondary Endpoint(s)

Wilcoxon signed-rank tests will be used to assess paired pre- and post-BCI peripheral blood measurements, and to assess paired post-BCI peripheral blood CD8⁺ T cell responses and T cell PD-1 expression in BAL effluent.

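### The signed-rank test planned for hypothesis 3 cannot show whether CD8+ response rises with BAL PD-1; replace it with a rank correlation adjusted for freeze time

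*Combined protocol and SAP*

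**What the plan says.** Section 3.2(2) states the hypothesis: "CD8+ T cell responses to BCI will be greater among subjects with high PD1 expressing T cells in BAL effluent". Section 10.2 lists it as the third statistical hypothesis, and the Protocol Summary lists the matching secondary endpoint as a correlation.

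The method is in section 10.4.4. It begins "Wilcoxon signed-rank tests will be used to assess paired pre- and post-BCI peripheral blood measurements", and then applies the same paired test to post-BCI CD8+ "T cell responses and T cell PD-1 expression in BAL effluent". Section 4.2.2 adds that the PD-1+ "cell percentage and transcriptome will be compared between responder categories", without defining the categories. Neither analysis has a dose term or stratum, and section 10.3 puts every treated participant in one analysis set.

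Freeze time is planned at seven levels from 1 to 30 seconds per site, assigned in order of enrolment under a 3+3 scheme (2.2.3, 6.1.2). Section 2.2.3 says the optimal duration is not known but that "longer freeze times may be needed in order to induce anti-tumor immune responses". In section 4.2.3 a subset analysis will "investigate if there is an optimal freeze time duration for inducing anti-tumor immune responses". Dose level enters the immune analysis only there and in section 10.4.7, for the pre-to-post CD8+ change. It is not used for the BAL PD-1 question.

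**The concern.** There are two faults, one behind the other.

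First, the test does not match the hypothesis. Hypothesis 3 is about association across participants: do those with higher BAL PD-1 respond more? A signed-rank test on within-participant differences between a blood response and a BAL expression level asks whether those differences are centred on zero. The answer depends on the scales of the two measurements, not on whether they move together.

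Second, a valid association test would still leave freeze time unaccounted for. The protocol treats freeze time as a possible driver of CD8+ response in one analysis and omits it from another with the same outcome. If response does vary with freeze time, that variation is noise in an unadjusted comparison with BAL PD-1. Because dose rises with enrolment order, a trend over time in BAL PD-1 would also line up with dose.

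At stake is a secondary result that could inform later anti-PD-1 combination studies. Section 10.5 gives the immune results that role, and section 10.4.1 still applies a 0.05 significance level to them.

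**Working it through.** **1. The plan's own power figure.** Section 10.5 gives 15 subjects, about 0.75 SD, within-subject correlation 0.5 and approximately 80% power. This is for the pre-to-post change; no power is stated for hypothesis 3.

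- SD of the difference = √(2 × (1 − 0.5)) = 1.
- Normal approximation, two-sided 0.05: 0.75 × √15 − 1.960 = 2.905 − 1.960 = 0.945, so power is 82.8%. The paired t test gives 77.1% and the signed-rank test about 75% (simulated).
- n for 80% power: ((1.960 + 0.842)/0.75)² = 13.95, so 14 (normal); 16 (t); about 17 (signed-rank).

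The stated figure is reproduced to within 2 patients. It says nothing about association with BAL PD-1.

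**2. Simulation set-up.** From the documents: the dose levels, and totals of 15 and 24 (section 5.6 gives 15-24). Fifteen patients are levels 1-5 × 3. Twenty-four are 7 × 3 plus 3 more at level 7. Assumed, because the documents give no values: BAL PD-1 (X) and CD8+ response (Y) have within-dose SD 1 and within-dose correlation ρ; Y shifts by k per SD of log freeze time; X drifts by d per SD along the same order; tests are two-sided at 0.05.

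**3. The planned signed-rank test of Y against X.**

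- Equal locations: it rejects in about 0-6% of runs, whether or not an association exists, including under shared drift.
- Locations 2 SD apart: it rejects in 99-100% of runs, including when ρ = 0.

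The result follows the location gap, not the association.

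**4. Dilution in an unadjusted association test (ρ = 0.5, d = 0).** Dose adds variance k² to a within-dose variance of 1, so the marginal correlation is ρ/√(1 + k²). At k = 1 this is 0.5/√2 = 0.35. Simulated power:

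| k | n=15 unadjusted | n=15 partial on dose | n=24 unadjusted | n=24 partial on dose |
|---|---|---|---|---|
| 0 | 43% | 40% | 68% | 65% |
| 0.5 | 34% | 40% | 54% | 62% |
| 1 | 21% | 37% | 33% | 61% |
| 1.5 | 14% | 36% | 23% | 59% |

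A rank-sum test of response between high and low BAL PD-1, split at the median, falls from 26% to 12% (n=15) and from 46% to 22% (n=24) between k = 0 and k = 1.

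**5. False positives (ρ = 0).** With only a dose effect or only drift, unadjusted Spearman stays near 5%. With both, the induced correlation is kd/√((1 + k²)(1 + d²)); at k = 1, d = 0.5 it is 0.5/√(2 × 1.25) = 0.32.

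| k, d | n=15 unadjusted | n=24 unadjusted |
|---|---|---|
| 0.5, 0.5 | 11% | 16% |
| 1, 0.5 | 22% | 36% |
| 1, 1 | 55% | 79% |

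A dose term brings these back to about 5-6%. A repeat of the Spearman and signed-rank settings with another seed and 4,000 runs each agreed to within about 2.5 points.

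**The case against.** The strongest reply is that the power and error figures describe Spearman correlation, which the plan does not use. That is correct. A reader might infer that, under the plan as written, dose variation hides the association or drift creates a false one. The documents do not support that inference: section 10.4.4 contains no association measure, and step 3 shows that the planned test responds to neither mechanism. The figures apply only to the test that should replace it.

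Three further limits stand.

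- Dilution is conditional. Sections 2.2.3 and 4.2.3 raise a dose-response as a possibility and give no size.
- A spurious association needs two trends together. Concomitant chemotherapy, immunotherapy or radiation (5.1) and two probe platforms (6.1.1) are possible sources of drift, but nothing in the documents shows that BAL PD-1 drifts. BAL is taken before BCI, so freeze time cannot alter it.
- The 30-fold range needs escalation to level 7. Fifteen participants at three per level reach level 5, a 10-fold range. The BAL analysis also uses a subset of unstated size (4.2.2), and a subset below 15 would lower every power figure.

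It can also be said that the plan disclaims power for secondary outcomes (10.4.1, 10.5) and that no dose or safety decision rests on hypothesis 3. This limits the importance of the point. It does not excuse a test that cannot answer its question, and low power is a reason to use a covariate that is assigned and recorded for everyone.

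**Conclusion.** The point holds in two parts. The first is unconditional: the signed-rank test in section 10.4.4 cannot show whether CD8+ response is greater when BAL PD-1 is high. The second is conditional: an unadjusted association test would be diluted by any dose-response. At an assumed within-dose correlation of 0.5 and a dose effect of 1 within-dose SD, power is about 21% rather than 37% at n=15, and 33% rather than 61% at n=24. Inflation of false positives is a contingent risk, not a demonstrated one.

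Even with adjustment, these power figures are modest, so the result should be read as exploratory. The change is worth making because it repairs the test and protects against dose-order effects with data the trial already collects.

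**What to change.** In section 10.4.4, replace the signed-rank test for hypothesis 3 with a partial Spearman correlation, or rank regression. It should relate pre-BCI BAL PD-1, kept continuous, to the pre-to-post change in the CD8+ phenotype, with assigned per-site freeze time in log seconds as covariate. Name the time point (day 7 or day 14), the marker combination and which of the two BAL sites is used. Report the result as an exploratory estimate with a confidence interval, and the unadjusted correlation as a sensitivity analysis.

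State two limits with it. In a 3+3, dose and calendar time cannot be separated, so the covariate absorbs both. Per-site seconds is also not total freeze exposure, because cycles scale with tumour diameter: 2 cm at 3 seconds and 6 cm at 1 second both total 6 seconds.

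The cost is a short revision to section 10.4.4, no new data and one degree of freedom, about 2-4 points of power if dose has no effect. A single log-seconds term is preferable to a seven-level dose factor, which costs more (n=24, within-dose correlation 0.5, linear model: 59% power against 71%).
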